5.5 Other Analyses

5.5.1 Other endpoints and/or parameters

5.5.1.1 Pharmacokinetics

The plasma concentrations of ZLP and its two major metabolites ([REDACTED]) will be summarized by scheduled sampling day for the PK-PPS using n, arithmetic mean, median, SD, minimum, maximum, geometric mean, geometric coefficient of variation (geoCV) and 95% Confidence Interval (CI) (assuming log-normally distributed data).

PK summaries will be based on observed value. No imputation will be done. The following rules will apply for PK data listings and summaries:

- Values below the LLOQ will be reported as BLQ
- Descriptive statistics of concentrations will be calculated if at least 2/3 of the individual data points at a timepoint are above the LLOQ. Values that are BLQ will be replaced by the numerical value of the LLOQ/2 in this instance.
- The 95% CI lower and 95% CI upper should be left blank if the SD (or equivalently, the geoCV) is 0
- The geoCV will be calculated using the following formula where SD is the standard deviation from the log-transformed data

$$\text{geoCV}(\%) = \sqrt{\exp(SD^2) - 1} \times 100.$$

Individual concentrations will be listed for the PK-PPS and will include the actual sampling time in days relative to the previous dose.

PK assessments in participants undergoing rescue therapy will be analyzed separately.

Plasma concentration data of Zilucoplan may be subjected to population pharmacokinetic analysis to derive population estimates of PK parameters and test the effect of various covariates such as age, weight, gender. Details of the analysis will be described in a separate Data Analysis

Plan (DAP). This analysis may be performed by combining the data from the current study with data from other Zilucoplan studies if deemed appropriate. The results of the population PK analysis will not be reported in the CSR but may be in a separate modelling report.

5.5.1.2 Pharmacodynamics

Pharmacodynamic analyses will be performed on the PD-PPS. The pharmacodynamic endpoint is the sRBC lysis assay.

Summary statistics will be provided for the values, change from baseline, and percent change from baseline at each of the scheduled assessment time points.

PD assessments in participants undergoing rescue therapy will be analyzed separately.

Population PD or population PK/PD analyses may be conducted for the PD variables of interest. Details of such PD or PK/PD analyses will be described in a separate DAP. The results of the analyses will not be reported in the CSR but may be in a separate report.

5.5.1.3 Time needed for administration of SC ZLP

The time needed for administration of SC ZLP will be analyzed using descriptive statistics as detailed in Section 5.1.

5.5.1.4 Participants' treatment satisfaction

The participants' treatment satisfaction is assessed via the TSQM-9 questionnaire. Descriptive analyses of the Effectiveness, Convenience and Global Satisfaction subscore will be displayed. Bar charts illustrating the mean and standard error at each visit by domain will be provided. Individual participant listings will be provided for all participants and for participants infected with COVID-19 as per the AE page. The details for the derivation of scores based on the TSQM-9 questionnaire are available in Section 6.1.5.6.

5.5.1.5 Participants' treatment preference

The participants' treatment preference is assessed via a single question where only one answer should be selected. If more than one answer is selected, the value will be set as Missing.

Descriptive analyses, as detailed in Section 5.1, will be used to analyze the participants' preference.

5.5.1.6 Genomics

No Genomics analysis is planned in this study.

5.6 Subgroup analyses

No subgroup analyses are planned in this study.

5.7 Interim Analyses

If ZLP is not commercially available in the US at the time of the last visit of the last participant in the Main Treatment Period, an interim analysis will be conducted. This interim analysis will include all data collected during the Main Treatment Period.

At the interim analysis, all TFLs concerning the Main Treatment Period only will be provided, unless otherwise stated.

If further interim analysis will be considered during the Main Treatment Period then this, will be of exploratory nature and only descriptive statistics will be provided.

At the final analysis, all the TFLs concerning the Main Treatment Period and the Overall Treatment Period will be provided, except:

- The by visits participant disposition and safety analyses will be displayed only on the Overall Treatment Period,
- The participant disposition and safety listings will be provided on the Overall Treatment Period.

5.8 Data Monitoring Committee (DMC) or Other Review Board

No DMC or Other review Board are planned in this study.

6 SUPPORTING DOCUMENTATION

6.1 Appendix 1 Non-key analysis specifications

6.1.1 Baseline characteristics and demographics

Participant demographics and baseline characteristics will be summarized for the mITT, using descriptive statistics. In case there is a difference of more than 5 study participants, those descriptive statistics will be duplicated in the SS.

Descriptive statistics for continuous variables (including n, mean, SD, Median, Min and Max) will be provided for:

- Age (years), calculated as (year of informed consent date – year of birth)
- Height (cm)
- Weight (kg)
- Body mass index (BMI) (kg/m^2) calculated as: $BMI = \frac{\text{Weight}(\text{kg})}{(\text{Height}(\text{m}))^2}$ using the weight and height measurements obtained at screening.
- Baseline MG-ADL and QMG scores

Descriptive statistics for categorial variables (including counts and percentages) will be provided for:

- Gender (Male/Female)
- Race (American Indian or Alaska native, Asian, Black, Native Hawaiian or other Pacific Islander, White, Other/Mixed)
- Ethnicity (Hispanic or Latino, Not Hispanic or Latino)
- Age (≤ 18 , 19- < 65 and ≥ 65 years).
- Geographic region (North America)
- Country

- BMI in kg/m² (<18.5, 18.5 - <25, 25 - <30, 30 - <35, 35- < 40, ≥ 40)
- Weight in Kg (<43, 43 - <56, 56- <77, 77 - <150, ≥ 150)
- MD-ADL scores (≤9/≥10)
- QMG scores (≤17 / ≥18)
- Chronic Kidney Disease Stages: normal renal function (Estimate glomerular filtrate rate (eGFR) ≥ 90 mL/min/1.73m²), mild (eGFR 60–89 mL/min/1.73m² [CKD stage 2]), moderate (eGFR 30–59 mL/min/1.73m² [CKD stage 3]), severe (eGFR 15–29 mL/min/1.73m² [CKD stage 4]) renal insufficiency end stage renal disease: eGFR < 15 mL/min/1.73m². A by-participant listing of Baseline characteristics will be provided.

6.1.2 Protocol deviations

Important protocol deviations (IPDs) are deviations from the protocol which could potentially have a meaningful impact on the study conduct, on the primary analysis, key safety or PK/PD outcomes for an individual participant. IPDs will be identified and documented prior to data base lock to confirm exclusion from analysis sets.

The summary of the IPDs will be performed for the Main Treatment Period as well as for the Overall Treatment Period in mITT.

Relationship to COVID-19 will be programmed from the COVID-19 Impact eCRF page or when available, it will be assessed by the sites.

A listing of the important protocol deviations will be provided for the Main Treatment Period as well as for the Overall Treatment Period in mITT population; a COVID-19 related flag will be present.

6.1.3 Medical history

6.1.3.1 Medical history (other than MG disease history)

Medical History will be summarized by SOC, HLT and preferred term (PT) for the mITT population. A participant will be counted only once for each preferred term. The summary will present the results alphabetically by SOC, HLT within SOC, and within HLT, by decreasing frequency for the PT.

Medical History will be listed on the ES population.

6.1.3.2 gMG disease history

The following gMG disease history data will be summarized for the mITT Population.

- Age at onset (years)
- Duration of disease (years) = (Date of Study Day 1 – Date of Diagnosis)/365.25

Note: If the Date of Diagnosis day and month are missing impute July 2nd, if only the day is missing impute the 15th. If the imputed Date of Diagnosis date is later than the date of Study Day 1, impute Study Day 1.

- Symptoms at onset (Ocular/Generalized)

Note: Generalized symptoms at onset: participants with respiratory symptoms or symptoms in the limb, bulbar or any other location; participants at this category might also have ocular symptoms at onset as well.

- MGFA Disease Class at Screening (Class II (IIa, IIb), III (IIIa, IIIb), or IV (IVa or IVb))
- Ever had a Crisis (Yes/No)
- Time since most recent crisis (months) = (Date of Study Day 1 – Date of crisis) / (365.25/12)

Note: If the Date of Crisis day and month are missing impute July 2nd, if only the day is missing impute the 15th. If the imputed Date of Crisis date is later than the date of Study Day 1, impute the date of Study Day 1.

- Crisis History (Number of crises: 1, 2, 3, more than 3)
- Reason for switching to study medication (Logistical challenges including travel and time spent at a hospital, Challenges with venous access, Lengthy intravenous infusion, Other)

gMG disease history characteristics will be listed overall.

6.1.4 Prior/concomitant/follow-up medications

6.1.4.1 Prior/concomitant medications classification

Medications will be classified as follow based on imputed start and stop dates & times as outlined in Section 5.1.1.10.

- **Past** medications will include any medications that started and stopped before the first administration of IMP.
- **Prior** medications will include any medications that started before the first administration of IMP.
- **Baseline** medications will include any medications that started prior to dosing and continued after (classified as prior and concomitant medications).
- **Concomitant** medications will include any medications that have been taken at least once after the first administration of IMP.
- **Concomitant Only** medications will include any medication that started after the first administration of IMP.

Table 6.1: Prior and Concomitant Medications

Medication Started	Medication finished	Classification
Before 1st Dose IMP	Before 1st Dose IMP	Past
Before 1st Dose IMP	Any time	Prior
Before 1st Dose IMP	After 1st Dose IMP	Baseline (= prior and concomitant)
Any time	After 1st Dose IMP	Concomitant
After 1st Dose IMP	After 1st Dose IMP	Concomitant Only

Where a medication start date is partially or fully missing, and it is unclear as to whether the medication is prior or taken at baseline, it will be assumed that it is taken at Baseline.

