**Table 1-2: Schedule of Activities**

Study Period	Screening Period a	Main Treatment Period						Extension Treatment Period	EW/ Withdrawal Visit b,w	SFU Visit (In-clinic) c	Rescue Therapy Visit (If applicable) d
		Baseline e (In-clinic)	Week 1 (Phone call)	Week 2 (In-clinic)	Week 4 (Phone call)	Week 8 (Phone call)	Week 12 (In-clinic)				
Visit name	Screening Visit (In-clinic)							Week 24, 36, 48... every 12 weeks (In-clinic)			
Visit #	1	2	3	4	5	6	7	8, 9, 10...	–	–	–
Day	-14 or -56	1	8	15	29	57	84	168, 252, 336...		(Last dose +40 days)	
Visit Window f	±3d	±2d	±2d	±2d	±2d	±2d	±2d	±7d		±7d	
Procedure/activity											

f The visit windows provided are with respect to the Baseline Visit with the exception of the SFU Visit, in which the visit window applies to 40 days after the last dose of study medication.

g Procedures performed as SOC during the Screening Period may be used to determine eligibility. Informed consent must be obtained prior to performing any study-specific procedures that are not SOC.

h Screening includes disease history with documented diagnosis of gMG by the MGFA criteria (Class II-IVa) and documented serology for AChR autoantibodies.

i Height will be measured only at Screening.

j All prescriptions and over-the-counter medications taken during the 30 days prior to Screening through the last study visit will be documented. Note: A complete history of medications taken for the treatment of gMG will be collected.

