## **6.5 Concomitant medication(s)/treatment(s)**

Concomitant medications include any prescription or over-the-counter medication that is ongoing on Day 1 or that is initiated following the first dose of study medication on Day 1.

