**Relative contraindications:**

- Curariform agents: use of nondepolarizing molecules of rapid degradation, such as atracurium, is possible but requires precise monitoring
- Benzodiazepines
- Neuroleptics (phenothiazine)
- Carbamazepine
- Lithium

IV C5 inhibitor must not be administered while the participant is receiving ZLP. If deemed needed as per the Investigator's judgment, study participant may be readministered their previous IV C5 inhibitor or administered a different IV C5 inhibitor after discontinuation of the study medication and completion of an EW/Withdrawal Visit. The participant should return for a SFU Visit 40 days ( $\pm 7$  days) after the last dose of ZLP.

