6.1.4.3 MG Specific Prior and Concomitant Medications

MG specific medication will be presented separately from the other prior and concomitant medications (for both tables and listings). A MG specific medication is defined by the “indication” value “Myasthenia Gravis” on the Prior and Concomitant Medication eCRF form. MG specific Past, Prior, Baseline, Concomitant and Concomitant only medications will be summarized on the SS as defined in Section 6.1.4.2.

Additionally, the number and percentage of participants who are taking one or more of the sets of MG specific medications presented in Table 6.2 (i.e., Groups A-H) will be summarized using the same 2 sets of tables: MG specific prior medications and MG specific medications taken at baseline.

Table 6.2: Medication class

Group	Medication	Preferred Term on Prior/Concomitant eCRF form	Reported Term on gMG Treatment History Form
A	Prednisone for gMG	PREDNISONE	PREDNISONE
	Other corticosteroids for gMG	DEXAMETHASONE METHYLPREDNISONE METHYLPREDNISONE SODIUM SUCCINATE PREDNISOLONE METHYLPREDNISOLONE HYDROCORTISONE TBD**	OTHER CORTICOSTEROIDS PREDNISOLONE METHYLPREDNISOLONE
B	Azathioprine	AZATHIOPRINE	AZATHIOPRINE
	Mycophenolate	MYCOPHENOLATE MOFETIL	MYCOPHENOLATE MOFETIL

Table 6.2: Medication class

Group	Medication	Preferred Term on Prior/Concomitant eCRF form	Reported Term on gMG Treatment History Form
		MYCOPHENOLATE ACID	
C	IVIG	IMMUNOGLOBULINS	INTRAVENOUS IMMUNOGLOBULIN
	SCIG	IMMUNOGLOBULINS	SUBCUTANEOUS IMMUNOGLOBULIN
D	PLEX* or Plasmapheresis	PLASMA EXCHANGE PLASMAPHERESIS	PLASMA EXCHANGE PLASMAPHERESIS
E	Cyclosporine	CICLOSPORIN	CYCLOSPORINE
	Cyclophosphamide	CYCLOPHOSPHAMIDE	CYCLOPHOSPHAMIDE
	Methotrexate	METHOTREXATE	METHOTREXATE
	Tacrolimus	TACROLIMUS	TACROLIMUS
	Rituximab	RITUXIMAB	RITUXIMAB
		TBD**	
F	Cholinesterase inhibitors	GALANTAMINE	GALANTAMINE
		PYRIDOSTIGMINE PYRIDOSTIGMINE BROMIDE	PYRIDOSTIGMINE
		AMBENONIUM	AMBENONIUM CHLORIDE AMBENONIUM CHLORURE MYTELASE
		NEOSTIGMINE	NEOSTIGMINE METHYLSULFATE NEOSTIGMINE BROMIDE
		DISTIGMINE	DISTIGMINE BROMIDE
G	C5 inhibitors	ECULIZUMAB	ECULIZUMAB
		RAVULIZUMAB	RAVULIZUMAB
H	FcRn	EFGARTIGIMOD ROZANOLIXIZUMAB	EFGARTIGIMOD ROZANOLIXIZUMAB

eCRF=electronic Case Report Form; gMG=generalized myasthenia gravis; IVIG=intravenous immunoglobulin; NOS=not otherwise specified; PLEX=plasma exchange; SCIG=subcutaneous immunoglobulin

*plasma exchange will be on the Procedures eCRF (if concomitant procedure).

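### The SAP's Concomitant classes have no end at the last zilucoplan dose, so MG therapy started afterwards, including a permitted return to an IV C5 inhibitor, is tabulated as concomitant with zilucoplan

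*SAP*

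**What the plan says.** SAP 6.1.4 is headed "Prior/concomitant/follow-up medications". Section 6.1.4.1 and Table 6.1 then define five classes: Past, Prior, Baseline, Concomitant and Concomitant Only. All five are anchored to the first dose. For the Concomitant class the rule is that such "medications will include any medications that have been taken at least once after the first administration of IMP". The narrower class, Concomitant Only, looks at the start date instead: such "medications will include any medication that started after the first administration of IMP". The last dose appears in none of the definitions, and there is no follow-up class.

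Protocol 6.5 is equally open: a concomitant medication is one "ongoing on Day 1 or that is initiated following the first dose of study medication on Day 1".

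On joint use, protocol 6.5.2 states that "IV C5 inhibitor must not be administered while the participant is receiving ZLP". It then lets a participant go back to the former product or be "administered a different IV C5 inhibitor after discontinuation of the study medication and completion of an EW/Withdrawal Visit", with the SFU Visit still due 40 (±7) days after the last dose. Under protocol 6.8, participants who decline the Extension, or who stop zilucoplan during it, move to standard of care outside the study and also have an SFU Visit to come.

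On recording, footnote j of protocol Table 1-2 reads: "All prescriptions and over-the-counter medications taken during the 30 days prior to Screening through the last study visit will be documented". On output, SAP 6.1.4.3 says that "MG specific Past, Prior, Baseline, Concomitant and Concomitant only medications will be summarized on the SS".

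**The concern.** This is a switch study. Every participant arrives on an IV C5 inhibitor, so a return to one is a foreseeable step for anyone who stops zilucoplan. A reader is likely to use the MG-specific concomitant table to see what other MG therapy was given alongside zilucoplan. Under the written rule, that table mixes two things: therapy given during zilucoplan, and therapy begun once zilucoplan had ended. An eculizumab or ravulizumab row could reflect a permitted switch back, yet the table alone would not distinguish it from joint use that the protocol bars. Likewise, IVIG begun after the last dose would add to the apparent use of extra MG therapy during zilucoplan.

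The SAP draws the missing boundary elsewhere. Section 5.1.1.1.1 marks days after the last dose with a plus sign, and 5.1.1.1.3.1 defines a follow-up period. Only the medication classes lack it.

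**Working it through.** No stated figure in the plan bears on this point, so the check applies the written rule to example records.

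**Inputs.** Class definitions: SAP 6.1.4.1 and Table 6.1. Recording period: protocol Table 1-2, footnote j. SFU timing: 40 ± 7 days after the last dose (protocol 6.5.2 and 6.8). Planned size: 20 (protocol 4.1). Assumed for illustration: first dose on Day 1, last dose on Day 50, and an Early Withdrawal Visit before Day 55.

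**Window.** 40 − 7 = 33 days and 40 + 7 = 47 days after the last dose. In the example the SFU Visit falls between Day 50 + 33 = Day 83 and Day 50 + 47 = Day 97. A medication started on Day 55 or Day 60 is therefore recorded.

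**Classification.**

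| Example record | Days | Rule as written | With an end at the last dose |
|---|---|---|---|
| IV C5 inhibitor, last infusion at Screening | −14 | Past, Prior | unchanged |
| IV C5 inhibitor restarted after zilucoplan | 55 to 90 | Concomitant, Concomitant Only | Follow-up |
| IVIG started after zilucoplan | 60 to 64 | Concomitant, Concomitant Only | Follow-up |
| IVIG rescue during zilucoplan | 30 to 34 | Concomitant, Concomitant Only | unchanged |
| Pyridostigmine, ongoing | before Day 1 to 90 | Prior, Baseline, Concomitant | unchanged |

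As written, rows two to four carry the same labels, so the tables cannot separate therapy during zilucoplan from therapy after it. With an end at the last dose, only the two records that begin after it move.

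**Size.** Shift in a table row = k / N, where k is the number of participants affected in that row and N is the Safety Set. With N = 20, k = 1 gives 1/20 = 5 percentage points. The documents give no value for k. As an assumed range, k = 2, 4 and 6 give 2/20 = 10%, 4/20 = 20% and 6/20 = 30%. Because medications are summarised by preferred term, these counts could split between eculizumab and ravulizumab rows.

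**Reach.**
- The Group A-H summaries in SAP 6.1.4.3 cover prior and baseline use only, so the C5 inhibitor group (Group G) is not distorted.
- Time to rescue and change in standard-of-care regimen have their own definitions in SAP 5.3.2 and do not use these classes. Nor does the MG-ADL analysis in 5.3.1.1.2.
- TEAEs are defined in SAP 5.4.2.1 by event date and dosing dates, not by medication class.
- Participants who move to commercial zilucoplan need no SFU Visit (protocol 4.4), so they have no such window.

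**The case against.** The case for leaving the text alone has four parts.

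1. **The SAP follows the protocol.** Protocol 6.5 has no end point either. This is true, and it means that a change in the SAP alone departs from the protocol definition and must be logged. It does not make the table clearer.

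2. **A window past the last dose matches the plan's own exposure concept.** SAP 5.4.1 counts time at risk to 40 days after the last dose to cover five half-lives, and TEAEs are counted to the same limit. A drug begun on day +5 might explain a TEAE on day +10, and would no longer be labelled concomitant. This point stands. It is a reason to keep such drugs visible under their own label, not to merge them with therapy given during zilucoplan.

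3. **The true timing can be found elsewhere.** Medication listings show the reported dates (SAP 6.1.4.2). Where relative day is shown, starts after the last dose carry a plus sign. Important deviations have their own summary and listing (SAP 6.1.2). Restarting an IV C5 inhibitor requires withdrawal from the study (protocol 7.2), and reasons for discontinuation are tabulated (SAP 5.2). With about 20 participants, a careful reader can reconstruct the sequence. This stands and limits the harm, but the tables themselves remain ambiguous.

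4. **The output specifications are in a separate document** (SAP 1) and might already separate later starts. That cannot be checked here. The SAP rule as written does not.

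A reader might go further and infer that permitted switch-backs would be counted as prohibited joint use, or that 10% to 30% of participants would wrongly appear on a concomitant C5 inhibitor. The documents support neither. The medication table is not the test for deviations, and the counts behind those percentages are assumptions.

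**Conclusion.** The point holds as a defect in a descriptive table. Under SAP 6.1.4.1 and Table 6.1, MG therapy started between the last zilucoplan dose and the SFU Visit is shown as Concomitant and Concomitant Only, and the follow-up class that the heading announces does not exist. It is more than a missing detail, because the stated rule yields a table open to misreading on a question central to a switch study.

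The size is 5 percentage points per affected participant in a given row if the Safety Set is 20. How many will be affected is unknown. The point rests on a literal reading of the rule and on medications being recorded through the SFU Visit. It would be tempting to conclude that the safety or efficacy results are biased. They are not: no endpoint, test, analysis set or TEAE count depends on these classes.

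**What to change.** - In SAP 6.1.4.1 and Table 6.1, limit Concomitant and Concomitant Only to medications taken at least once between the first and the last IMP dose, both included.
- Define Follow-up as medications started after the last IMP dose, and tabulate it separately for MG-specific medications.
- Record the change in SAP 6.3 as a refinement of the open-ended definition in protocol 6.5.
- Keep Follow-up medications in the listings, so that drugs begun within the 40-day TEAE window remain visible when those events are reviewed.

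The default in SAP 5.1.1.10, that a medication with ambiguous dates counts as concomitant, can stay.

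No new data are needed, because the dates are already collected. The cost is SAP wording, one programming rule, one more class and table, and a documented departure from the protocol wording.
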